## **2.e Risks and Benefits**

### **Risks:**

A likely or common mild risk that may occur from participating in the testing sessions and/or participating in any exercise program for 12 weeks is that participants may experience muscle soreness or fatigue. Participants will have planned rest breaks, be allotted any unplanned rest breaks requested, and be encouraged to maintain hydration levels during exercise training. There is also a mild risk of emotional distress or discomfort in completing the questionnaires. Participants will complete questionnaires in

---

a private area and will be allowed to decline to answer any of the questions that make them uncomfortable.

An uncommon risk that may occur is an exercise-related injury, such as muscle strain or sprain. To help ensure that participants are safe to exercise, they will be required to have a physician's referral to participate in this study; in addition, a heart rate monitor and accelerometers will be worn during selected testing and exercise sessions (if assigned to the CBEI) to ensure accurate monitoring of their health status. They will also be educated about the proper and safe way to exercise before the study begins. For CBEI participants, trained research members will be present during all sessions to ensure participant safety. Proper precautions to avoid injury, including stretching and rest breaks, will be employed to reduce the risk of soft tissue damage.

Another risk to participants includes potentially dangerous conditions associated with SCI, such as autonomic dysreflexia, during assessments and exercise training. However, this is a very small risk. All research team members are familiar with serious conditions, such as autonomic dysreflexia, and medical precautions to monitor any life-threatening conditions will be taken during testing and training. In the highly unlikely event a participant experiences a medical emergency, immediate appropriate actions will be taken by research staff.

**Benefits:**

Participants may or may not benefit from being in this study. Participants may directly benefit by:

- Increasing their ability to exercise and function in the community
- Improving their cardiorespiratory and metabolic function
- Improving their psychological well-being
- Increasing their physical fitness
- Receiving new and valuable information about exercise recommendations and their health

**2.f Early Withdrawal of Subjects**

Participants (CBEI or EEG) will be withdrawn if they are non-compliant with the exercise program specific to their group assignment (miss >30% of visits in a particular month) or if they experience a medical complication that prohibits exercise.

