## A Introduction

### A1 Study Abstract

Persons with spinal cord injury (PwSCI) are at a greater risk for major health conditions and poorer health outcomes than persons without spinal cord injury. For PwSCI, habitual exercise is critical for both physiological and psychological well-being. Prior research indicates that exercise programs conducted in a controlled setting have positive effects on the physical and psychosocial fitness of PwSCI, but the efficacy and feasibility of these programs are not well understood in community-based settings. PwSCI will be randomized to a 12-week community-based exercise intervention (CBEI; n = 20) or an exercise education control group (EEG; n = 20). The proposed project aims to examine

---

potential health benefits in response to the intervention and identify the barriers and facilitators to successful implementation of a CBEI in PwSCI (N = 40).

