## **E Study Design**

### **E1 Overview or Design Summary**

The proposed project utilizes a mixed-methods approach. An experimental strategy using an RCT (single-blinded) will be used. Forty participants ( $n = 40$ ) will be randomized into the CBEI ( $n = 20$ ) or the EEG ( $n = 20$ ) by a research staff member who will not be involved in either conducting outcome assessments or implementation of the intervention. This design will assist in reducing variability and maximizing the effect size for powering a subsequent larger RCT.

The intervention for participants in the CBEI will consist of one-on-one, formally directed exercise sessions by trained staff in the PQHWC. The CBEI is based on the recent evidence-based exercise guideline for PwSCI, American College of Sports Medicine's (ACSM) Physical Activity Recommendations for PwSCI, best available evidence, and preliminary work. The intervention will include 36 60–90-minute sessions over 12 weeks (three sessions/week) with a goal of participants guiding their own exercise regimens by the end of the intervention. Personalized exercise sessions will be created for each participant based on fitness goal(s), preferred exercise equipment, and results from their initial assessment. Participants will be educated on how equipment works and what exercises are appropriate, and will be guided on intensity levels. At the beginning of each session, vitals and pain will be assessed, and each participant will complete a minimum 5-minute warm-up. After the warm-up, each participant will complete cardiovascular training in bouts of at least 10 minutes. Staff will monitor the sessions to ensure that participants perform at least 30 minutes three times a week of moderate-to-vigorous exercise, as determined by a report of 12 or higher on the Borg's Rate of Perceived Exertion (RPE) Scale (6–20). Due to altered sympathetic innervation in PwSCI, target heart rate may not be reliable; therefore, RPE will be the real-time determinate of intensity. Activity monitors (GT9X Actigraph, Pensacola, FL) will be donned to capture intensity data to be processed post hoc. Each participant will then complete a 3–5-minute cool-down. After cardiovascular training, each participant will complete strength training geared toward their goals, with guidance from PQHWC staff

---

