to perform a comprehensive variety of strength exercises to promote fat-free mass, muscle endurance, and overall strength. Staff will set up and monitor strength training to ensure that, for each exercise, participants perform at least two to three sets of 10–15 repetitions (reps) at 50%–75% one-rep max (1RM) for each exercise targeting functioning muscle groups. After strength training, participants will complete a 5–10 minute cool-down, and final heart rate, blood pressure, and pain will be assessed. Staff are occupational therapists and physical therapy assistants who have worked in an exercise setting with PwSCI. Staff will be taught the exercise guidelines and exercise session protocols using written materials, demonstration, and practice sessions. Following each exercise intervention session, participants will describe what they liked and did not like, provide a rating (1–5) of how much they gained from the session, and answer an open-ended item requesting suggestions for improvement. At the end of each session, the trainer will rate the participant's perceived participation during the session (1–6) using the Pittsburgh Rehabilitation Participation Scale.

The participants in the EEG will complete an intervention that consists of a one-on-one, hour-long educational session orienting participants to an online resource center, the National Center on Health, Physical Activity, and Disability (NCHPAD). NCHPAD promotes health and well-being for PwD through resources such as adapted exercise videos, information on accessible fitness equipment, personalized exercise videos tailored to PwD, and an individualized 14-week exercise program. Participants will be given an overview of NCHPAD and asked to identify resources of interest on the website. Each participant will be asked to use resources on NCHPAD to engage in physical activity for 12 weeks. Each participant will receive a weekly phone call to inquire about their physical activity, exercises engaged in, RPE during exercise, and whether any resources were used.

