**2.g When and How to Withdraw Subjects**

The research coordinator of the study is primarily responsible for scheduling testing and exercise sessions for participants. The research coordinator will also be in weekly contact with designated PQHWC staff to update the research team on the attendance/compliance of CBEI participants. If deemed that a participant is non-compliant with the exercise program protocol, the research coordinator will contact the participant and inform him/her of the withdraw policy. If the participant remains non-compliant over the following two weeks, he/she will be withdrawn by the research team and will be contacted via phone.

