## **G Statistical Plan**

### **G1 Sample Size Determination and Power**

This is a pilot study, with our primary interests in outcome variability and co-variability and estimates of feasibility and acceptability, which will aid in the planning of a larger trial. The sample size of 40 participants was selected to provide enough participants to assess the research protocol, determine trends in change, and provide data to calculate sample sizes for a larger RCT.

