**Aim 2:** We will use descriptive statistics to report on scales collected during and after sessions to further understand acceptability, feasibility, and fidelity. Our qualitative interviews will allow us to further explore whether patterns can be identified in participants who achieved improvement versus those who did not and those who dropped out of the study. Interview data will be transcribed, processed using NVivo, and analyzed using an adaptation of grounded theory analysis, which will include four steps to be employed iteratively: (1) open coding, in which particular concepts in the transcripts are identified and grouped into categories; (2) axial coding, in which categories are associated and related by conditions, actions/interactions, and consequences; (3) process coding, in which concepts and categories are examined in changing circumstances; and (4) selective coding, in which conceptual models and theories are developed, integrated, and refined.

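### Withdrawing participants from the study for poor monthly attendance selects on the adherence that the pilot is meant to estimate, and the rule's month, two-week test and EEG count are undefined

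*Combined protocol and SAP*

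**What the plan says.** **The rule.** Section 2.f applies to both arms and withdraws anyone who is "non-compliant with the exercise program specific to their group assignment (miss >30% of visits in a particular month"), or who has a medical complication that rules out exercise. Section 2.g first has the coordinator contact the participant, and then: "If the participant remains non-compliant over the following two weeks, he/she will be withdrawn by the research team". Section 2.h says that a withdrawn participant has no follow-up assessment, although a close-out contact about the reasons may be requested.

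**The visits.** E1 gives the CBEI arm 36 "sessions over 12 weeks (three sessions/week"). The EEG arm receives a "one-on-one, hour-long educational session orienting participants to an online resource center", and after that: "Each participant will receive a weekly phone call to inquire about their physical activity".

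**The purpose.** G1 gives the pilot's "primary interests in outcome variability and co-variability and estimates of feasibility and acceptability". G3 adds adherence and tolerance under the Secondary Aim. For Aim 2, G4 will use "descriptive statistics to report on scales collected during and after sessions to further understand acceptability, feasibility, and fidelity", together with interviews meant to compare improvers, non-improvers and dropouts. F4 places the experience interview at the first day of the T2 assessment. No section states a denominator for attendance.

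**The concern.** Adherence is one of the quantities the pilot should deliver, and the rule uses it to decide who remains under observation. People with a poor month leave, their later attendance and session ratings never arise, and they do not reach the visit at which the experience interview is held. A larger trial planned on attendance among those who remain would start from a figure that is too high.

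The rule is also not well enough defined to be applied in the same way to everyone. *Month* could be a calendar month, a 4-week block or a running window. The two-week check has no threshold. *Visits* has no stated meaning in EEG. Sections 2.f and 2.g differ on whether the trigger alone leads to withdrawal.

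**Working it through.** The documents give no expected attendance, withdrawal rate or power, so there is no figure of the plan's own to reproduce beyond 12 weeks × 3 = 36 sessions.

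**1. When the rule triggers in CBEI.** Assume a 4-week month, so 12 sessions. 30% of 12 = 3.6, so the trigger is 4 missed (4/12 = 33%); 3 missed (25%) does not trigger. Assume that remaining non-compliant means more than 30% of the next 6 sessions: 0.3 × 6 = 1.8, so 2 missed.
- Smallest total ending in withdrawal under 2.f alone: 4/36 = 11%.
- Smallest total with the 2.g step: (4 + 2)/36 = 17%.
- Three missed in each month: 9/36 = 25%, never triggers.

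So 17% missed can lead to withdrawal while 25% missed does not. The definition of a month matters here: a month holding 13 sessions triggers at 4 (31%), one holding 14 at 5 (36%).

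**2. EEG.** If weekly calls count, 0.3 × 4 = 1.2, so the trigger is 2 of 4 (50%), against 33% in CBEI. If only the education session counts, months 2 and 3 have no visits to miss. The sections on monitoring do not settle this: 2.g and G2 have gym staff report on CBEI compliance, while F6 6.a has them report on EEG compliance, although no EEG session is placed at the gym.

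**3. Effect on attendance.** Assumed inputs: of 20 in CBEI, 15 finish at 85%, and 5 are withdrawn at week 6 (18 sessions) after attending 60%.
- Completers: 15 × 36 × 0.85 = 459 sessions, 85%.
- All planned sessions, later ones counted as not attended: (459 + 5 × 18 × 0.60)/(20 × 36) = 513/720 = 71%.
- Had the five continued at 60%: (459 + 5 × 36 × 0.60)/720 = 567/720 = 79%.

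Removing the five therefore accounts for 85 − 79 = about 6 points. The further step from 79% to 71% comes from scoring their unavailable sessions as missed. With 3 withdrawn instead of 5, the figures are 85%, 552.6/720 = 77% and 585/720 = 81%.

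**4. Effect on ratings.** With one rating per attended session, finishers (75% of the arm) supply 459/513 = 89% of ratings under the rule and 459/567 = 81% without it.

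**5. A second model.** 200,000 simulated participants, true attendance 80%, the two-week test as in step 1, and no test possible after month 3.

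| Assumed miss rates | Withdrawn | Attendance among the rest |
|---|---|---|
| 20% for everyone | 13% | 81% |
| Beta(2,8), mean 20% | 22% | 85% |
| Beta(1,4), mean 20% | 25% | 88% |

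The upward shift is about 1 point if everyone is alike and 5 to 8 points if people differ in how often they miss.

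**The case against.** Several points on the other side stand.

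- **The rule does count misses.** The 2.g step softens it considerably: at a uniform 20% miss rate, 50% of participants would trigger 2.f at least once, but 13% would be withdrawn under the reading used above.
- **Earlier data are not lost.** Attendance and session ratings up to withdrawal are kept, a close-out contact may collect reasons, and a forced withdrawal is itself a feasibility result. Aim 2 also draws on monitors and staff views. The close-out contact is optional, however, and is not the T2 interview.
- **EEG could be counted.** The 2.f wording ties compliance to each arm's own programme, and the weekly calls could serve. The defect is that no count is defined, not that none is possible.

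A reader might infer three stronger things that the documents do not support.

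- *That someone attending 9, 9 and then 0 of 12 sessions must be kept.* This needs month 3 to be judged only at week 12. With the weekly contact in 2.g and the daily monitoring in F6 6.a and G2, the fourth miss would fall in week 10 and the two weeks would end in week 12, within the programme.
- *That the rule inflates attendance by 14 points (85% against 71%).* More than half of that gap comes from how post-withdrawal sessions are scored. Nor does any section say that attendance will be reported for completers only.
- *That the rule guarantees the hypothesis of acceptance and feasibility.* Neither C2 nor G4 sets a cut-off to pass.

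**Conclusion.** The concern holds in a limited form. Applied as written, 2.f to 2.h end observation on the basis of adherence in a pilot that is meant to estimate adherence. They can remove someone who missed 17% of sessions while keeping someone who missed 25%. The 17% and 25% rest on a 4-week month, and the 17% also on the assumed two-week test.

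The likely bias in attendance among those who remain is upward: about 6 points in the worked illustration (4 with three withdrawn) and 1 to 8 points in the simulation. All of these depend on assumed attendance. Under the rule neither available figure (85% or 71%) recovers the 79% that would have been seen without it.

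Two points need no assumption about attendance: *visits* is undefined for EEG, and holding the experience interview at T2 with no follow-up after withdrawal conflicts with the Aim 2 plan to learn from dropouts. The loss of T2 outcomes for the group comparison is a separate question and is not weighed here.

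**What to change.** 1. **Sections 2.f to 2.h:** separate non-attendance from study withdrawal, so that people who attend poorly stay in the study for data collection and attendance becomes an Aim 2 outcome. Leave medical withdrawal and the 2.g contact call as they are.
2. **G4, Aim 2:** report sessions attended out of 36 for everyone randomised to CBEI, and show any forced withdrawals beside that figure as a feasibility result. Summarise session ratings within each participant first, then across participants.
3. **F4 and 2.h:** offer the experience interview to those who stop, in line with the Aim 2 plan.
4. **If the sponsor keeps the rule:** reconcile 2.f with 2.g, define the month and the two-week test, and either take EEG out of the visit-based rule or state what is counted there. Make F6 6.a, 2.g and G2 agree on whose compliance the gym staff report.

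The cost is protocol wording, one reporting denominator and a few extra interviews. The downside is that some session slots stay with poor attenders and reported attendance will be lower.

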**2.g When and How to Withdraw Subjects**

The research coordinator of the study is primarily responsible for scheduling testing and exercise sessions for participants. The research coordinator will also be in weekly contact with designated PQHWC staff to update the research team on the attendance/compliance of CBEI participants. If deemed that a participant is non-compliant with the exercise program protocol, the research coordinator will contact the participant and inform him/her of the withdraw policy. If the participant remains non-compliant over the following two weeks, he/she will be withdrawn by the research team and will be contacted via phone.

**2.h Data Collection and Follow-up for Withdrawn Subjects**

Whether participants withdraw voluntarily or are withdrawn by research staff, they may be asked to complete a close-out visit (in-person or on the phone) to provide the research team with feedback regarding why they decided to leave the study early/not comply with the program.

---

As this is a pilot RCT, if a participant is withdrawn, initial assessment data will be evaluated; however, no follow-up assessment will be conducted.

### ***E3 Study Drug***

The proposed study is not a drug-trial intervention, but rather an exercise intervention using a developed community-based exercise intervention program.

#### **3.a Description**

Not applicable, this is not a drug study.

#### **3.b Treatment Regimen**

Not applicable, this is not a drug study.

#### **3.c Method for Assigning Subjects to Treatment Groups**

Not applicable, this is not a drug study

#### **3.d Preparation and Administration of Study Drug**

Not applicable, this is not a drug study

#### **3.e Subject Compliance Monitoring**

Not applicable, this is not a drug study

#### **3.f Prior and Concomitant Therapy**

Not applicable, this is not a drug study

#### **3.g Packaging**

Not applicable, this is not a drug study

#### **3.h Blinding of Study Drug**

Not applicable, this is not a drug study

## **F Study Procedures**

### ***F1 Screening for Eligibility***

Potential participants may either be approached or identified by the PI from Paraquad's waiting list; potential participants may also contact us after viewing a study flyer posted within community and rehabilitation facilities. The study coordinator may describe the study with participants over the telephone or in person and, if they are interested, verbal consent will be obtained to continue with the screening document. This process will be the same for all populations, as the randomization does not occur until after the first assessment is completed. After the screening document is complete, the study coordinator will obtain medical referrals from the participant's physician(s); once permission from the participant's physician(s) is received, the participant will be contacted via phone by the study coordinator and scheduled for their first assessment appointment.

---

## **F2 Schedule of Measurements**

The research coordinator will primarily schedule all initial and post-assessments with participants over the phone once participants are deemed eligible for participation. Prior to the scheduled initial assessment, a copy of the written consent form may be mailed to the potential participants so they may have time to review it, become familiar with it, and prepare any questions they may have. The research coordinator may also contact potential participants via phone 24–72 hours prior to their scheduled initial assessment to remind potential participants of their upcoming initial assessment appointment.

## **F3 Visit 1**

Upon arriving to their first assessment appointment, a research staff member will review the written consent form with the potential participant. Potential participants will be given time to review the form additionally on their own, discuss with family members if they wish, and have any and all questions addressed. Potential participants will then be asked to initial, sign, and date the form, as necessary, prior to participating further in the initial assessment. Once written consent is obtained, all participants will complete the initial assessment.

The initial assessment (T1) will be completed over two separate days, with the second day (D2) being completed within 10 days of the first assessment day (D1).

### **Procedures for Day 1 of Initial Assessment (T1D1):**

T1D1 (90–120 minutes) will be completed at Washington University’s EMC research laboratory, located within the Paraquad Health and Wellness Center building. During this appointment, participants will complete many self-report measures. These measures will assess: demographics (CORE), psychosocial factors (PROMIS–fatigue, depression, pain, sleep, and emotional support), physical activity (LTPAQ-SCI, ESES, and RM-4), and community participation (CPI). Participants will also be asked to perform functional mobility (6MPT), strength testing (BTE and Equalizer), and a cardiovascular fitness test (VO2peak). Resting blood pressure and heart rate, height, weight, and body mass index will also be measured on T1D1. The participants may be asked to wear a heart rate monitor and accelerometers to measure their intensity levels during testing.

